#### Appendix 1. Global Data and Safety Monitoring Committee

**Global Data and Safety Monitoring Committee (DSMC):** This independent committee will not include representatives of the trial sponsors, trial committees or trial centers, and will not include any doctors Trial Sponsor are directly responsible for the treatment of individual monkeypox patients.

Interim trial analyses will be monitored by the DSMC. Otherwise, the trial sponsor, collaborators, and administrative staff (except those Trial Sponsor produce the confidential analyses) will remain ignorant of the interim results.

The DSMC will, at intervals decided by itself, examine confidential interim analyses of safety and efficacy, reporting them to the executive group only if the DSMC considers them likely to require publication or a change in the conduct of the trial. Otherwise, the trial sponsors, trial committees, and trial centers will remain blind to the interim findings.

The protocol states that the evidence on mortality must be strong enough, and the range of uncertainty around the results must be narrow enough to affect national and global treatment strategies. It also states that realistic, appropriate sample sizes could not be estimated at the start of the trial; that it may be possible to enter several thousand hospitalized patients with the relatively mild disease when admitted and a few thousand with severe disease, yielding results that are separately reliable for each; and that the response to certain treatments may differ substantially between different populations or sub-populations (e.g., patients with particular prior conditions, older adults, patients in one or another large country).

In the light of this, the DSMC will independently evaluate the interim analyses and will inform the Executive Group of the Steering Committee if at any stage the results are, in the judgement of the DSMC, sufficiently robust for general release (ie, strong enough and with a sufficiently narrow range of uncertainty around the findings to affect national and global treatment strategies). The DMSC will decide independently how best to respond to interim analyses of safety and apparent efficacy, and what further such analyses to require.

Although the DSMC will be informed of each such SAE and SUSAR and major protocol violations as the trial office deals with reporting it, the DSMC may chiefly be concerned not with each individual event, but with the confidential analyses of the accumulated evidence on all such events. In light of this, the DMSC will decide independently how best to respond to the evidence on adverse reactions.

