#### Data collected electronically immediately before randomisation:

- o Country, geographic region of residence, hospital and randomizing doctor
- Confirmation that informed consent was obtained from the patient (or a surrogate/ representative)
- Age, sex and (yes/no): HIV, TB, malaria, hypertension, diabetes mellitus, asthma, hepatitis, hyperlipidemia, cancer, heart failure, renal disease, liver disease, chronic obstructive pulmonary disease (COPD), COVID-19, neoplasm, obstructive sleep apnea, obesity, immunosuppressive disorder other than HIV, sickle cell anemia, concurrent bacterial infections such as urinary tract, ear nose and/or throat, pulmonary, central nervous system, skin or gastrointestinal infection, bacteremia/sepsis or other.
- Date of onset of symptoms, date of hospitalization, and (yes/no) current/planned use of a few drugs
- Monkeypox lesions status (yes/no): at least one active, not yet scabbed, monkeypox lesion, other.
- o Current symptoms (yes/no): nausea, vomiting, abdominal pain, anorexia, cough, lymphadenopathy, dysphagia, fever, headache, ocular lesions, and buccal ulcers.
- Smallpox vaccination status (yes/no) or presence of vaccination scar (yes/no).
- Risk factors for monkeypox infection (yes/no): recent contact with known monkey pox case, type of contact, residing or visiting an area with an active monkey pox outbreak, animal handling.

**Trial entry; randomization:** A participant will be considered enrolled beginning from when the informed consent form is signed and randomization to an assigned treatment has occurred. Once enrolled, study drug administration will begin according to study group assignment. Participants will be randomized to one of the experimental treatments (k in number) for which they are eligible (no specific exclusion criteria) or to one of the placebos that correspond (in appearance, dosing interval, and route of administration) to each of those treatments. The randomization ratio will ensure that

participants have the same chance of receiving a placebo as they have of receiving each individual treatment for which they are eligible. All participants will also receive local SOC that is standardized at each site according to local/site guidance.

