#### **Appendix 2. Trial Governance**

The trial sponsor will invite the research institutions to join the trial. Within each country, one of the research institution would act as co-chief investigators of the trial.

**International Steering Committee:** This will govern the conduct of the trial in accordance with the agreed international protocol, amended as necessary during the study. Sites that do decide to join will, in consultation with trial sponsor, appoint one member to the international steering committee. Sponsor would seek the collaboration of appropriate local research sites at various health facilities. These members from each country would be jointly responsible for obtaining rapidly, at national and at the local hospital level, ethical approval and any other relevant permissions, and for encouraging Trial participation by the collaborating sites.

**Executive group of the steering committee:** For practicality, a smaller executive group of about 5-9 members of this committee will be set up in consultation with trial sponsor. They will confer electronically at frequent intervals with trial sponsor to ensure the study is being conducted appropriately by the team within trial sponsor and to ensure the trial steering committee is appropriately informed and consulted.

**TRIAL SPONSOR trial center (XXXXXX):** This will be responsible for the conduct of the trial. It will establish and maintain a web-based service for randomization, for receiving electronic reports of any SAEs and SUSARs for entry of follow-up information, and for sending reminders when follow-up is overdue. The trial center will help deal with obtaining all necessary approvals, recruiting and motivating centers, ensuring drug supplies, and reporting SUSARS. It will monitor recruitment rates, follow-up rates, data plausibility, and overdue follow-up, describing and regularly discussing with the executive group all aspects of the progress of the trial, but not conducting interim analyses of trial results.

Global Data and Safety Monitoring Committee (DSMC): This independent committee will examine confidential interim analyses of safety and efficacy, reporting them to the executive group only if the DSMC considers them likely to require publication or a change in the conduct of the trial. Otherwise, the trial sponsors, trial committees, and trial centers will remain blind to the interim findings.

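### Appendices 1 and 2 let the DSMC pass interim results, not just a recommendation, to the Executive Group for changes short of publication, and keep nothing closed for drugs still recruiting.

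*Protocol*

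**What the plan says.** Protocol, Appendix 1, gives the DSMC the task to "examine confidential interim analyses of safety and efficacy". On disclosure, it describes the committee as "reporting them to the executive group only if the DSMC considers them likely to require publication or a change in the conduct", meaning in how the trial is run. The next sentence sets out who stays blind: "Otherwise, the trial sponsors, trial committees, and trial centers will remain blind to the interim findings". Appendix 2 repeats both sentences in its paragraph on the DSMC.

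Appendix 1 then describes reporting a second time. The DSMC "will inform the Executive Group of the Steering Committee if at any stage the results are, in the judgement of the DSMC, sufficiently robust", the standard being whether they are fit to be made public. It also "will decide independently how best to respond to interim analyses of safety and apparent efficacy".

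Appendix 2 describes the recipients. The Executive Group is about 5-9 members of the International Steering Committee. Of its dealings with the sponsor it says: "They will confer electronically at frequent intervals with trial sponsor to ensure the study is being conducted appropriately". It also has to see that the Steering Committee is kept informed. The Steering Committee governs the trial under an "agreed international protocol, amended as necessary during the study". Appendix 1 recalls that realistic sample sizes could not be set at the outset.

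SOP-2 (Trial entry; randomization) allocates among k drugs, each with a matching placebo, so that "participants have the same chance of receiving a placebo as they have of receiving each individual treatment", counting only the drugs open to that participant.

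**The concern.** The usual safeguard is that a monitoring committee sends those who run a trial a recommendation and keeps the comparative data to itself until a comparison is to be closed or published. Here the stated object of the report is the analyses. One of the two triggers is a change in how the trial is run, which presupposes that recruitment continues in at least part of it. The assurance of blindness covers only the case in which no report is made. Nothing says what stays closed afterwards, for which drugs, or from whom.

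The stake is operational bias in comparisons still open. If the Executive Group and, through it, the sponsor have seen interim results by arm, later decisions on sample size, arms or sub-populations can no longer be shown to be independent of those results. The exposure is greater than usual because the size of this trial is to be settled while it runs and several drugs may be recruiting together.

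**Working it through.** The protocol gives no figure on this point to reproduce. The check is a reading of the text, followed by simple algebra on what a report could reveal.

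**1. The text**

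| Question | Appendix 1 | Appendix 2 |
|---|---|---|
| What is reported? | The interim analyses | The same |
| When? | If publication or a change in conduct is likely to be needed | The same |
| Limited to the drug concerned? | Not stated | Not stated |
| Who stays blind after a report? | Not stated; blindness is promised only otherwise | The same |
| Is a full report compelled? | No; the DSMC chooses its response | Not stated |

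If the report is the full set of analyses, every comparison is exposed for any k, and no algebra is needed.

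**2. Does the allocation imply a common control?** For a participant eligible for all k drugs, the SOP-2 rule gives each drug 1/(k+1) and all placebos together 1/(k+1). Assuming the placebo share is split equally, each matched placebo gets 1/[k(k+1)]:

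| k | Each drug | All placebos | Each matched placebo | Drug : own placebo |
|---|---|---|---|---|
| 2 | 33.3% | 33.3% | 16.7% | 2:1 |
| 3 | 25% | 25% | 8.3% | 3:1 |
| 4 | 20% | 20% | 5% | 4:1 |

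A drug would outnumber its own placebo k to 1, which points to pooled placebos. SOP-2 does not say that they are pooled.

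**3. What a one-drug report reveals.** Assumptions: placebos are pooled, every participant is eligible for every drug, and the overall event rate is known. Then

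overall = (placebo + sum of the k drug rates)/(k+1),

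mean of the other k-1 drugs = [(k+1) x overall - placebo - A]/(k-1).

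Illustrative rates (assumed): placebo 6%, drug A 5%.

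- k=2, other drug 3%: overall = (6+5+3)/3 = 4.67%. Recovered: 14 - 6 - 5 = 3%, which is exact.
- k=3, others 3% and 6%: overall = 20/4 = 5%. Recovered: (20 - 6 - 5)/2 = 4.5%, the mean only.
- k=4, others 3%, 6% and 4%: overall = 24/5 = 4.8%. Recovered: (24 - 6 - 5)/3 = 4.33%, the mean only.

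If participants are eligible for different sets of drugs, the arms no longer have equal weight and the identity fails. Without pooled placebos, a one-drug report shows only that drug and its own placebo.

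**The case against.** The strongest reply is that the clause restricts rather than obliges. It says when a report may be made, and Appendix 1 leaves the response to the DSMC, which could send a bare recommendation or confine itself to one drug. That stands: disclosure is permitted, not required.

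Second, results judged fit for general release are about to become public, so telling the Executive Group is no leak. That stands too, and it confines the point to changes short of publication.

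Third, a reader might infer that a shared placebo group means one report necessarily unblinds the remaining drugs. The protocol does not support this. SOP-2 describes matching placebos without saying they are pooled, k is not fixed, and the ratio depends on each participant's eligibility. Nor does it say that the overall rate circulates. Appendix 2 has the trial center discuss progress with the Executive Group but rules out its conducting interim analyses.

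Fourth, a reader might infer that the Executive Group's parent committee itself amends the protocol, or that results reach the sites. Appendix 2 does not name who amends, SOP-9 requires sponsor agreement and ethics approval before an investigator departs from or changes the protocol, and no text sends results to sites.

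Fifth, a DSMC charter or other core text, not available here, may set the form of reports. That is possible. A stricter charter would, however, sit badly with a rule that both appendices state in the same terms, so the wording would still need to change.

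**Conclusion.** The point holds as a gap in a stated rule. Both appendices make the interim analyses the thing reported, allow this for changes short of publication, and protect nothing for drugs still recruiting once a report is made. No bias is shown to have occurred, and its size cannot be estimated from the protocol.

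The possible exposure runs from complete, if the report covers all drugs, down to one drug and its own placebo, if the report is confined and placebos are analysed separately. In between, pooled placebos expose the control result for open drugs. With two drugs, equal eligibility and a known overall rate, the other drug's rate follows exactly. With three or more drugs, only the mean of the others does. What is exposed is comparative results by arm, not individual allocations.

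The change is worth making because it is cheap and protects comparisons the trial has yet to answer.

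**What to change.** In Appendices 1 and 2, replace the reporting clause with wording to this effect:

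- The DSMC sends the Executive Group a recommendation: continue, close a drug, or make a specified change.
- Results by arm are released only for a drug whose results the DSMC judges robust enough for general release, or whose randomisation is to close.
- Results for drugs still recruiting stay closed to the Executive Group, the sponsor and the centres, whether or not a report has been made.

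The DSMC charter should say the same. The cost is a few sentences. The downside is that, for changes short of closure or publication, the Executive Group acts on a recommendation without seeing the numbers.

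One limit remains. If placebos are pooled, releasing results for a closed drug still shows the control result. A rule that later decisions be taken only by people who have seen no interim data would not cure this, since after publication nobody in governance would qualify, so none is proposed.

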#### **Appendix 2. Trial Governance**

The trial sponsor will invite the research institutions to join the trial. Within each country, one of the research institution would act as co-chief investigators of the trial.

**International Steering Committee:** This will govern the conduct of the trial in accordance with the agreed international protocol, amended as necessary during the study. Sites that do decide to join will, in consultation with trial sponsor, appoint one member to the international steering committee. Sponsor would seek the collaboration of appropriate local research sites at various health facilities. These members from each country would be jointly responsible for obtaining rapidly, at national and at the local hospital level, ethical approval and any other relevant permissions, and for encouraging Trial participation by the collaborating sites.

**Executive group of the steering committee:** For practicality, a smaller executive group of about 5-9 members of this committee will be set up in consultation with trial sponsor. They will confer electronically at frequent intervals with trial sponsor to ensure the study is being conducted appropriately by the team within trial sponsor and to ensure the trial steering committee is appropriately informed and consulted.

**TRIAL SPONSOR trial center (XXXXXX):** This will be responsible for the conduct of the trial. It will establish and maintain a web-based service for randomization, for receiving electronic reports of any SAEs and SUSARs for entry of follow-up information, and for sending reminders when follow-up is overdue. The trial center will help deal with obtaining all necessary approvals, recruiting and motivating centers, ensuring drug supplies, and reporting SUSARS. It will monitor recruitment rates, follow-up rates, data plausibility, and overdue follow-up, describing and regularly discussing with the executive group all aspects of the progress of the trial, but not conducting interim analyses of trial results.

Global Data and Safety Monitoring Committee (DSMC): This independent committee will examine confidential interim analyses of safety and efficacy, reporting them to the executive group only if the DSMC considers them likely to require publication or a change in the conduct of the trial. Otherwise, the trial sponsors, trial committees, and trial centers will remain blind to the interim findings.

**Add-on studies:** The trial involves only a simple characterization of patients and outcomes. So, within particular countries, some sites participating in the trial may choose to collaborate with each other in more detailed studies. Such add-on studies should not analyze trial treatment allocation in relation to the main trial outcomes until after the main trial findings have been published in the names of all collaborators. Apart from that, the planning, conduct, and reporting of any such studies are independent of trial governance.

#### Appendix 3. Protocol amendment history

Version	Date	Description of main amendments
		0
		0
		0
		0
